2.6.1 Secondary endpoint(s)

There are three efficacy secondary objectives:

- 1. Between treatment comparison of XXB750 highest dose versus placebo in reducing the mean 24hr SBP from baseline at Week 12.
- 2. Between treatment comparison of XXB750 highest dose versus placebo in reducing the average of the mean 24hr SBP from baseline at Week 9 and at Week 12.

3. To determine a dose-response signal and to characterize the dose-response relationship in XXB750 doses and placebo with respect to the proportion of participants achieving BP control at week 12.

2.6.2 Statistical hypothesis, model, and method of analysis

The efficacy variable in secondary objective 1 is the change from baseline at Week 12 in the mean 24hr SBP and will be analyzed using a repeated measures ANCOVA model with treatment, number of background antihypertensive medications (=3 vs >3), region stratification factor (with Japan combined into Asia), visit (Week 9 or Week 12), and treatment-by-visit as factors, and baseline mean 24hr SBP as a covariate, with a common unstructured covariance matrix among visits. The analysis time point for the treatment comparisons is at Week 12. Please refer to Section 1.2.2 and Section 2.5.3 for the intercurrent events and its handling strategy and Section 2.5.4 for handling missing data not related to intercurrent event. The analysis will be run on each of the imputed datasets as described in Section 2.5.2. Overall results, including adjusted mean change at Week 12 within each treatment arm, the difference in mean change at Week 12 between XXB750 dose arm and placebo, its 95% confidence interval (CI), are obtained by applying Rubin's rules on the estimates obtained from imputed datasets.

[figure not shown]
If the mentioned model above does not converge, the model will be modified by replacing the common unstructured covariance matrix with a compound symmetric matrix between treatment groups and provide the mentioned estimates above.

[figure not shown]
The efficacy variable in secondary objective 2 is the average change from baseline at Week 9 and Week 12 in the mean 24hr SBP and will be analyzed using an analysis of covariance (ANCOVA) model including treatment, number of background antihypertensive medications (=3 vs >3), and region stratification factor (with Japan combined into Asia) as fixed-effect SBP factors and baseline mean 24hr as covariate. Please refer to Section 1.2.2 and Section 2.5.3 for the intercurrent events and its handling strategy and Section 2.5.4 for handling missing data not related to intercurrent event. The analysis will be run on each of the imputed datasets as described in Section 2.5.2. Overall results, including adjusted mean change at Week 12 within each treatment arm, the difference in mean change at Week 12 between XXB750 dose arm and placebo, its 95% confidence interval (CI), are obtained by applying Rubin's rules on the estimates obtained from imputed datasets.

Dose response results (proportion with/without placebo subtracted and corresponding 95% CI) based on model averaging over all models in the candidate sets as described in Section 2.5.2 will be presented. In addition, a logistic model will be fitted to the response variable at Week 12 based on imputed datasets with treatment (placebo and XXB750 dose groups), number of background antihypertensive medications (=3 vs >3), and region stratification factor (with Japan combined into Asia) as factors, and the baseline mean 24hr SBP and mean 24hr DBP as covariates. Estimates (proportion with/without placebo subtracted and corresponding 95% CI) from logistic model are combined based on Rubin's rule and presented alongside model averaging estimates. Figure of dose-response shape based on model averaging will also be displayed.

Number and percentage of participants with ambulatory BP control will be summarized by treatment group for observed values. Figures will be produced to visually show the observed ambulatory BP control by visit over 12 weeks randomized treatment period for each treatment group.

The analysis will be based on all participants in FAS.

The statistical testing procedure described below will be carried out for the multiple treatment comparisons in the primary and secondary efficacy objectives to ensure that the overall significance level for the multiple hypotheses to be tested is controlled at the one-sided 0.025 level (i.e. two-sided 0.05).

The testing hypotheses associated with secondary efficacy objectives are described below:

- **H**₂₀: No difference in the change of mean 24hr SBP from baseline at Week 12 between highest XXB750 dose versus placebo.
- H₃₀: No difference in average change of mean 24hr SBP from baseline at Week 9 and at Week 12 between highest XXB750 dose versus placebo.
- **H**₄₀: There is no dose-response relationship for XXB750 (i.e. the dose response relationship is flat) in terms of proportions of participants achieving blood pressure control at Week 12.

The testing procedure is to be based on the sequentially rejective multiple test procedure prespecified in controlling overall type I error (Bretz et al 2009) and H₁₀ of the primary hypothesis will be initially test first at the one-sided 0.025 significance level. If the primary hypothesis can be rejected, the relocation of its significance level with a weight of 1 to the other hypotheses is specified in Figure 2-3 below. The sequentially rejective multiple test procedure is completed until no more hypothesis can be further rejected.

Figure 2-3 Sequentially rejective multiple testing procedure

2.6.3 Handling of intercurrent events

For Ambulatory BP control, participants with intercurrent events will be imputed as not having BP control. Refer to Section 2.5.3 for other secondary estimands intercurrent event handling.

2.6.4 Handling of missing values not related to intercurrent event

Refer to Section 2.5.4

2.6.5 Sensitivity analyses

The secondary analysis using retrieved dropouts or missing at random (MAR) approaches for missing values after early treatment/study discontinuation due to adverse event(s) or death may assign values in the XXB750 dose groups that are too favorable. Therefore, a sensitivity analysis will be performed where missing values after early treatment/study discontinuation due to AE or death will be multiply imputed based on results from similar participants in the placebo group. Placebo multiple imputation method described in Section 2.5.6 will be performed, where participants randomized to XXB750 dose groups are assumed to be similar to placebo treated participants after drop-out.

2.6.6 Supplementary analyses

The supportive analyses for the secondary analysis results are listed below:

- 1. Analysis based on the while on-treatment strategy to handle the intercurrent of premature discontinuations of study treatment will be performed. This analysis uses the last on-treatment data defined in Section 2.1.1 as the Week 12 assessment and repeat the analysis described in Section 2.6.2. This analysis will only be performed when premature treatment discontinuation occurs in more than 10% of FAS participants.
- 2. Subgroup analyses (region and race excluded due to small sample size) will be performed for the first secondary efficacy analysis. The analysis will be done using the analysis specified in Section 2.6.2 at individual subgroup level separately. If convergence issue arises, then the subgroup category will be combined with another one for subgroups with more than two categories. Otherwise, subgroup analysis will not be performed. Please see Section 2.2.1 for subgroup details.

2.7 Safety analyses

For all safety analyses, the safety set will be used. All listings, figures and tables will be presented by treatment group.

Safety data to be analyzed are listed as below:

- Adverse events (AE) and Serious Adverse events (SAE)
- Adverse events of special interest (AESI): Serious hypotension, Serious hypersensitivity reactions, and Serious injection site reactions, Severe tachycardia, Severe acute bradycardia, Serious presyncope/syncope
- Safety topics that are potential risks: Hypotension, Hypersensitivity reactions, Injection site reactions, Tachycardia, Bradycardia,
- Safety topics that are neither AESI nor Potential risks: Renal toxicity and Hepatotoxicity
- Laboratory assessments
- Vital signs, e.g. weight, systolic blood pressure (SBP), diastolic blood pressure (DBP), and pulse rate.

2.7.1 Adverse events (AEs)

Any AE that occurred during the study period will be included in AE summary tables by the specific treatment period as described in Table 2-2, i.e., AEs that occurred in one of the following periods: (1) run-in period, (2) randomized treatment period, (3) safety follow-up period, and (4) randomization period (randomized treatment period and safety follow-up period).

The analysis will consider all participants in the Run-in set (RIS) for AEs reported during the run-in period and Safety set (SAF) for reported AEs during the randomization period, randomized treatment period and safety follow-up period.

Table 2-2 Allocation of AEs (randomized treatment period and safety follow-up period listed separately from randomization period)

Screeni ng visit (V1)	Placebo run-in (V20-V30)	Randomize d treatment (V100-V170)	Safety follow- up (V180- V1999)	Phase AE to be reported in
		* Random	ization period	
X				Reported by site from informed consent;
	X			Report AE in Placebo run-in
	X	X2		Report as two separate AEs:
				One with onset date X for Placebo run-in and one with onset date X2 for Randomized treatment (also randomization period);
	X		X2	Report as two separate AEs:
				One with onset date X for Placebo run-in and one with onset date X2 for Safety follow-up (also randomization period)
	X	X2, X3		Report as two separate AEs:
				One with onset date X for Placebo run-in and one for Randomized treatment period (* Randomization period) with corresponding onset date and severity depending on analysis
	Χ	X2 X3	Report as thre	ee separate AEs:
			One with onse	et date X for Placebo run-in,
			treatment, an Safety follow- * One for	randomization period with g onset date and severity
	X	X2, X3		separate AEs:
	•	,	One with onse and one Randomizatio	et date X for Placebo run-in for Safety follow-up (* n period) with corresponding and severity depending on
	Χ	Υ	•	Report as two separate AEs:
				One with onset date X for Placebo run-in and one with onset date Y for Randomized treatment (also randomization period)
	X		Υ	Report as two separate AEs:
				One with onset date X for Placebo run-in
				and one with onset date Y for Safety follow- up (also randomization period)
	X	Y, Y2		Report as two separate AEs: One with onset date X for Placebo run-in

Screeni ng visit (V1)	Placebo run-in (V20-V30)	Randomize d treatment (V100-V170)	Safety follow- up (V180- V1999)	Phase AE to be reported in
		* Random	ization period	
				and one for Randomized treatment (* Randomization period) with corresponding onset date and severity depending on analysis;
	X	Υ	Y2	Report as three separate AEs:
				One with onset date X for Placebo run-in,
				one with onset date Y for Randomized treatment, and one with onset date Y2 for Safety follow-up;
				* One event for Randomization period with corresponding onset date and severity depending on analysis
	X		Y, Y2	Report as two separate AEs:
				One with onset date X for Placebo run-in
				and one for Safety follow-up (* Randomization period) with corresponding onset date and severity depending on analysis;
	Χ	ΥZ	Report as thre	ee separate AEs:
			One with onse	et date X for Placebo run-in,
			treatment, ar Safety follow-	·
			 One ever Randomization 	nt with onset date Y for
	Χ	Y Z, Z2		ee separate AEs:
	~	1 2, 22	•	et date X for Placebo run-in,
			one with on treatment, an	set date Y for Randomized d one for Safety follow-up with g onset date and severity
				nt with onset date Y for
		X		Report one AE X in Randomized treatment period (* Randomization period)
		X, X2		Report as one AE for Randomized treatment (* Randomization period) with corresponding onset date and severity depending on analysis
		X	X2	Report as two separate AEs:
				One with onset date X for Randomized treatment and one with onset date X2 for Safety follow-up;

Screeni ng visit (V1)	Placebo run-in (V20-V30)	Randomize d treatment (V100-V170)	Safety follow- up (V180- V1999)	Phase AE to be reported in
		* Random	ization period	
				* One event for Randomization period with corresponding onset date and severity depending on analysis
		X	Υ	Report as two separate AEs:
				One with onset date X for Randomized treatment
				and one with onset date Y for Safety follow-up;
				* One event with onset date X for Randomization period
		X	Y, Y2	Report as two separate AEs:
			,	One with onset date X for Randomized treatment
				and one for Safety follow-up with corresponding onset date and severity depending on analysis;
				* One event with onset date X for Randomization period
			Х	Report AE X in safety follow-up period (*Randomization period)
			X, X2	Report as one AE:
				One for Safety follow-up (*Randomization period) with corresponding onset date and severity depending on analysis

X stands for onset date of AE. Y is the same PT which onsets after the end date of X. Similarly, Z is the same PT which onsets after the end date of Y.

X2/Y2/Z2 stands for the same PT but with an increased severity over X/Y/Z respectively X3 stands for the same PT but with an increased severity over X2.

Treatment emergent adverse events (new or worsened) during a specific period (run-in, randomization, randomized treatment or safety follow-up) are defined as any recorded AE with its start date (recorded or imputed) later than or equal to the start date of the specific period as defined below:

- 1) Run-in period: injection date of single-blinded placebo.
- 2) Randomization period: first date of study treatment injection.
- 3) Randomized treatment period: first date of study treatment injection.
- 4) Safety follow-up: 1+ max(end of treatment (EOT) disposition, Week 12 EOT visit date)

The incidence of treatment-emergent adverse events (new or worsened) will be summarized by primary system organ class, preferred term, severity, and relationship to study drug according to the Medical Dictionary for Regulatory Activities (MedDRA). The latest MedDRA version before database lock will be used for reporting the study.

Within each reporting period (run-in period, randomized treatment period, safety follow-up period or randomization period, see Table 2-2), the following rules are applicable. If a participant reports more than one adverse event with the same preferred term, the adverse event with the greatest severity will be presented. If a participant reports more than one adverse event within the same primary system organ class, the participant will be counted only once with the greatest severity at the system organ class level, where applicable. Statistical analyses, which will be performed for the randomization period and other periods as appropriate, will include all AEs with onset date during the defined period and up to the analysis cut-off irrespective of how long after the last day of study treatment they occurred.

The number and percentage of participants reporting any adverse event during each reporting period will be summarized by primary system organ class, preferred term and treatment. The most common adverse events reported ($\geq 5\%$ in any group for each preferred term in the SOC-PT table) will be presented in descending frequency according to its incidence in the XXB750 highest dose group starting from the most common event.

Separate summaries, for each reporting period, will be provided for study medication related adverse events, deaths, serious adverse events, other significant adverse events leading to permanent study discontinuation. AESI and Potential risks will be summarized separately in addition to the above analysis. Please see Section 2.7.1.1 for details.

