The randomized treatment period begins at the time of randomization and ends with the max(end of treatment (EOT) disposition, Week 12 EOT visit date). During the randomized treatment period, participants will return for scheduled clinic visits. For all related safety analyses, randomized treatment starts with the first administration of randomized, double-blind study drug.

Safety follow-up period

The safety follow-up period begins one day after max(end of treatment (EOT) disposition, Week 12 EOT visit date), and ends on the date of EOS. For participants whose EOS visit is on/before Week 12 and for those who do not take study treatment at all during randomized treatment period, they should not have safety follow-up period calculated, i.e., start date and end date for safety follow-up should be missing.

Randomization period

The randomization period is the combination of the randomized treatment period and the safety follow-up period.

Study exposure

The study exposure means the exposure for the randomization period. The duration of study exposure (days) is defined as the date of end of study minus the date of randomization plus one.

Baseline for randomized treatment period

Only assessments performed prior to first dose of randomized treatment period are considered for baseline. Unless specified otherwise, baseline for the randomized treatment period is defined as the measurement obtained at the end of run in (Visit 30) or randomization visit (Visit 100) whichever occurs last, or the measurement obtained at an earlier visit (scheduled or unscheduled) which was closest to the Visit 30/Visit 100, if Visit 30/Visit 100 measurement is missing.

For OBPM, baseline derivation is based on measurements eligible for analysis, as specified in Section 2.12.1

Baseline for randomization period

Randomization period is the total duration of randomized treatment period and the safety follow-up period. Therefore, the definition of baseline for randomization period will be the same as the baseline for randomized treatment period.

Baseline for safety follow-up period

Unless otherwise specified, baseline for safety follow-up period is defined as the measurement obtained at the EOT visit (Visit 170) or the measurement obtained closest to the EOT visit if the measurement at EOT is missing.

Baseline for run-in period

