2.2 Analysis sets

The following analysis sets will be defined for statistical analysis:

Screened set (SCR) - All participants who signed the informed consent form. The SCR includes only unique screened participants, i.e., in the re-screened participants only the chronologically last screening data is counted.

D Somme

Run-in set (RIS) - All participants who have signed the informed consent and received at least one dose of single-blind run-in medication drug.

Randomized analysis set (RAS) - All randomized participants who received a randomization number, regardless of receiving trial medication.

Full analysis set (FAS) - All participants to whom study treatment has been assigned by randomization and who are not mis-randomized. Mis-randomized participants are those who have not been qualified for randomization, have been inadvertently randomized into the study and did not receive any double-blind study medication. According to the intent to treat principle, participants will be analyzed according to the treatment they have been assigned to during the randomization procedure.

Safety set (SAF) - All randomized participants who received at least one dose of double-blind study treatment. Participants will be analyzed according to the study treatment received, where treatment received is defined as the randomized/assigned treatment if the participant took at least one dose of that treatment or the first treatment received if the randomized/assigned treatment was never received.

Rules leading to exclusion from specific analysis sets of participants are provided in Appendix 5.5.

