3.1 Primary endpoint(s)

The study is planned to randomize 170 participants including approximately 10% lost to follow-up, allocated in the ratio of 1:1:1:1:1 to placebo, XXB750 30 mg SC q4w, 60 mg SC q4w, XXB750 120 mg SC q4w and XXB750 240 mg SC q4w, respectively.

Assuming a common standard deviation of 12 mmHg for mean 24hr SBP change from baseline and a one-sided 2.5% significance level (with adjustments for multiple comparisons using MCP-MOD), a sample size of 150 participants (30 each in placebo, XXB750 30 SC q4w, XXB750 60 mg SC q4W, and XXB750 120 mg SC q4w, and XXB750 240 mg SC q4w) will provide a minimum power of 92% if the underlying true maximum mean 24hr SBP reduction on XXB750 vs placebo is 10 mmHg.

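### Safety follow-up AE percentages are set over the whole Safety Set, so participants who left the study by Week 12 are counted as event-free in a period the SAP says they do not have

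*SAP*

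**What the plan says.** SAP 2.7.1 summarises adverse events by period. After randomization the set is the "Safety set (SAF) for reported AEs during the randomization period, randomized treatment period and safety follow-up period", and the opening of SAP 2.7 makes the Safety Set the general rule for safety analyses. The required output is a count and a percentage for every period: "The number and percentage of participants reporting any adverse event during each reporting period will be summarized by primary system organ class", then by preferred term and treatment.

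SAP 2.2 defines the Safety Set as "All randomized participants who received at least one dose of double-blind study treatment". Nothing in that definition depends on how long a participant stayed in the study.

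SAP 2.1.1 then removes the follow-up period for some participants. The rule reads "For participants whose EOS visit is on/before Week 12 and for those who do not take study treatment at all during randomized treatment period", and for these people "they should not have safety follow-up period calculated, i.e., start date and end date for safety follow-up should be missing".

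The only drop-out figure is in SAP 3.1 (repeated in protocol 9.9.1): "The study is planned to randomize 170 participants including approximately 10% lost to follow-up".

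**The concern.** Two rules in the SAP do not fit together. One puts every treated participant into the follow-up AE tables. The other says that some treated participants have no follow-up period. If both are followed as written, those participants sit in the denominator without ever being able to reach the numerator.

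The SAP avoids this for the run-in. There it uses the Run-in Set, which consists of people who received the run-in injection and so entered that period. Follow-up has no matching set.

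Safety over the 20 weeks, follow-up included, is a stated secondary objective. Protocol 4.1 explains the follow-up by the drug's long half-life and the need for participants to come off it safely. The follow-up table is the one that isolates that time. If its percentages are diluted, the late AE burden looks smaller than it was among the people actually followed.

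**Working it through.** **Who is affected.** Of the two groups named in SAP 2.1.1, those never treated are already outside the Safety Set. That leaves Safety Set members with an end-of-study visit on or before Week 12. Stopping treatment alone does not put someone in this group, because protocol 4.1 keeps treatment discontinuers in the study and requires both follow-up visits. There is one exception. The same section places the last visit 12 weeks after the last dose, so a person who stops after the first injection could have an end-of-study visit at Week 12 and lose the period.

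**Why they cannot be in the numerator.** SAP 2.7.1 counts an event as treatment-emergent in a period only if it starts on or after the period's start date, which for follow-up is built from "Safety follow-up: 1+ max(end of treatment (EOT) disposition, Week 12 EOT visit date". Taken alone, that expression could return a date for an early leaver with an end-of-treatment disposition. SAP 2.1.1 says the date is to be missing, so no event can be assigned.

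**Nothing else corrects it.** The exposure-adjusted rates and Kaplan-Meier estimates in SAP 2.7.1.1 cover selected safety topics in the randomized treatment period only.

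**The plan's own figure.** 30 evaluable per arm with 10% loss: 30 / (1 − 0.10) = 33.3, rounded up to 34; 5 × 34 = 170. This reproduces the stated 170.

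**Formula.** Let N be an arm's Safety Set, d the share with no follow-up period, and r the AE risk among those who have one.
- Events counted = r × N × (1 − d)
- Percentage reported = r × N × (1 − d) / N = r × (1 − d)
- Relative understatement = d; absolute understatement = r × d

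**At d = 10%** (every planned loss is a Safety Set member who leaves by Week 12; values of r are assumed, since the documents give none):

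| r | Reported | Points lost |
|---|---|---|
| 5% | 4.5% | 0.5 |
| 10% | 9% | 1 |
| 20% | 18% | 2 |
| 30% | 27% | 3 |

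**Range over assumed d, at r = 20%.** d = 0: no loss. d = 5%: 1 point. d = 20%: 4 points. d = 30%: 6 points.

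**In whole participants.** With 34 in the Safety Set and 4 leaving, 6 people with an AE is 6/30 = 20.0% of those followed and 6/34 = 17.6% of the Safety Set. Three people is 3/30 = 10.0% against 3/34 = 8.8%. Here d = 4/34 = 11.8%, above 10% because 33.3 was rounded up to 34.

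**Between arms.** With equal true risk, the ratio of reported percentages is (1 − d₁) / (1 − d₀), which is 1 when exit is equal. With assumed exits of 5% and 20% and r = 20% in both arms: 0.20 × 0.95 = 19% and 0.20 × 0.80 = 16%, ratio 0.84. With 0% and 30%: 20% and 14%, ratio 0.70. These exit rates only illustrate the range.

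**The case against.** *The SAP never names a denominator.* It names the participants to be considered, and the missing follow-up dates are just the flag a programmer could use to form a period-specific N. This is true as far as it goes. But no section tells the programmer to do so, and the stated analysis-set rule leads to the full Safety Set.

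*The restricted denominator has its own bias.* Events over all treated participants keep the randomised comparison. Restricting to those who reached follow-up conditions on something that happened after randomization: if poor tolerability drives exit, the arm is represented by those who tolerated the drug. This stands as a real downside, and it is the reason to show both numbers. It does not justify counting unobserved people as event-free.

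*Early leavers are also unobserved for part of the other periods, where the full Safety Set is accepted.* The cases differ. In those periods each member contributes some time at risk. In follow-up the leavers contribute none, by the SAP's own definition.

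*The effect is small and the tables are descriptive.* This stands. No formal between-arm test of follow-up AEs is planned. At 34 per arm, the standard error of a difference between two 20% rates is √(2 × 0.20 × 0.80 / 34) = 9.7 points, far above the 3 points in the 5% v 20% illustration. The randomization-period tables also cover the 20 weeks and are not touched by this problem. SAP 2.3.1 tabulates study discontinuation by arm, so a careful reader could see how many had left.

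*A reader might infer that the distortion hides an excess at the highest dose.* The documents do not support that. They give no exit rate by arm, and intolerance that leads only to stopping treatment leaves the participant in follow-up.

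**Conclusion.** The point holds, at modest size. Following SAP 2.7.1 and 2.1.1 together counts Safety Set members who left by Week 12 as event-free in the follow-up AE tables. Each arm's follow-up percentage is too low by the factor (1 − d).

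On the planned loss, the understatement is at most about 10% in relative terms. That bound assumes that all planned losses are treated participants who leave by Week 12. The planning figure covers losses in general, and protocol 7.4 allows a participant not to be declared lost until the end of the study, so the share is probably smaller. Any one-dose stoppers whose end-of-study visit falls at Week 12 would add to d, and the documents do not say how many to expect. A reader might take 12% from 30 of 34 remaining; the excess over 10% comes from rounding the arm size up and is not a planned loss rate.

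Whether the comparison between arms is distorted depends on unequal exit, which cannot be judged from the documents. AE counts and the tables for the randomized treatment and randomization periods are unaffected.

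**What to change.** In SAP 2.7.1, state that percentages for the safety follow-up period use as denominator the Safety Set participants with a non-missing follow-up start date. Show that n beside the Safety Set N in each arm's column header. Keep the full Safety Set for the randomized treatment and randomization periods.

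The cost is one sentence and a changed column header in the follow-up tables. No new data are needed and the efficacy analyses are untouched. Because the follow-up percentages will then describe only people who entered follow-up, a footnote should direct the reader to the randomization-period table over the Safety Set and to the study discontinuation table.
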